2.1 Recruitment and representativeness of recruited patients

A CONSORT flow chart will be constructed (Moher et al) – see Figure 2. This will include the number of eligible patients, number of patients agreeing to enter the trial, number of patients refusing, then by trial arm: the number continuing through the trial, the number withdrawing, the number lost to follow-up and the numbers excluded/analysed. The reasons for ineligibility/numbers not consenting following screening will be shown, as will the reasons for not being randomised following baseline.

Figure 2. Template CONSORT diagram for TENDAI trial

2.2 Baseline comparability of randomised groups

The measured baseline variables are given in section 1.8.1. Baseline variables will be described by trial arm and overall: means and standard deviations/medians and interquartile ranges for continuous variables that are normally distributed/not normally distributed, and frequencies and proportions for binary or categorical variables. The list of baseline variables we will describe is as follows: recruitment site, age, sex, relationship status, educational level attained, for those that have attained less than secondary school: years of primary school completed and years of secondary school completed, whether the participants have a job that provides income, whether the participants have a job that provides goods, occupational class, likely coded as unemployed/unskilled/skilled non-professional/professional, 1st, 2nd or 3rd line ART prescribed. No statistical testing of the baseline differences between randomised groups will be done.

2.3 Completion of allocated treatment, treatment fidelity and treatment experience

2.3.1 Completion of allocated treatment and treatment fidelity

The number of therapy sessions attended by participants in the TENDAI arm will be reported using the median and interquartile range.

We define completing the TENDAI treatment as completing at least four therapy sessions. Sessions are given in a pre-specified order such that a participant can only complete the fourth session of therapy once they have completed the first, second and third sessions of therapy, in that order. There is no definition of completion of therapy in the EUC arm. We will summarise the number and proportion completing at least four therapy sessions.

2.3.2 Treatment experience

The number and proportion of participants withdrawing from treatment only not the overall trial (for withdrawals, please see section 2.4) will be summarised for the TENDAI group only as well as by their reasons for withdrawing from treatment.

2.4 Loss to follow-up and other missing data

The number and proportions of participants missing each primary and secondary outcome variable will be summarised by trial arm and overall at each time point. The numbers and proportions withdrawing from the trial (i.e. actively state they are unwilling to provide any further research data) will be summarised by their reasons for withdrawal from the trial at each assessment time point by trial arm and overall.

2.5 Adverse event reporting

Adverse events (AE), and serious adverse events (SAE) will be summarised as number of events and number of people having events by trial arm and overall.

2.6 Scoring of questionnaire outcomes

See Appendix 1 for details on scoring of all outcome measures.

2.7 Descriptive statistics for outcome measures

The primary and secondary outcomes will be summarised at baseline, 4, 8 and 12 months, where the outcome is recorded at that timepoint (see sections 1.8 and 5 for details of the timepoints at which measures are recorded), these are: proportion with viral suppression, PHQ-9 score, adherence measured using (a) self-report, (b) pharmacy refill, and log viral load. Means and standard deviations or medians and interquartile ranges will be used for the continuous PHQ-9 and self-report adherence variables. Frequencies and proportions will be used to describe the binary/categorical viral suppression and adherence variables. We will also summarise the frequency and proportion of individuals switching medications between each time point.

3. Data analysis plan – Inferential analysis

3.1 Main analysis of treatment differences

The main statistical analyses will follow the intention to treat principle as much as possible. The senior statistician will remain fully blind until an initial draft of the primary analysis report is complete and needs to be checked. The trial

statistician will be unblinded. Group difference estimates between TENDAI and EUC and associated 95% confidence intervals will be reported from models appropriate to the measurement schedules and nature of the outcome in question, i.e. depending on whether the outcome is continuous or categorical. The models that will be used are outlined in the following sections. Where the outcome variable is recorded at baseline it will generally be included in the analysis model as a covariate unless stated otherwise. The significance level for the difference between TENDAI and EUC on the primary outcome will be 5% (two-sided). This significance level will also be used for the secondary outcomes, but the reader will be alerted regarding the impact of multiple testing.

Previous therapy trials (e.g. Everitt et al) have found that the post-randomisation completion of therapy variable was predictive of missingness of the primary outcome. We will therefore consider multiple imputation (MI) for the primary outcome only if there are post-randomisation variables that predict missing primary or secondary outcome data (see section 3.1.4.5 for the variables that will be considered). We will not consider multiple imputation where there are no post-randomisation variables that predict missing data, nor will we consider MI if less than ten percent of the outcome data are missing (Dong and Peng). The former is the usual/recommended approach in trials where independent variables (i.e. trial arm, time point, stratification factors) are generally complete, and imputing missing outcomes only adds variability/noise (Sullivan et al). For outcomes which are measured repeatedly, missing data in post randomisation assessments will be handled by fitting mixed models using maximum likelihood methods. Valid inferences are provided by this method assuming that the missing data mechanism is ignorable, that is, missing at random (MAR) and providing that all predictors of missing data are included as covariates in the model. To include such predictors of missing data, we will assess pre-specified baseline variables (see Section 3.1.4.5 Missing outcome data) to identify which measures are predictive of missing outcomes. If we use multiple imputation, these baseline variables will be included in the imputation but not analysis models. If we do not use multiple imputation, we will include these baseline variables as additional independent variables in the PHQ-9, self-report adherence and log viral load outcome analysis models described in sections 3.1.1 and 3.1.2. More detail on the handling of missing data can be found in section 3.1.4.5.

3.1.1 Analysis of primary outcome

The viral load data will be coded into a binary variable as follows: <1000 copies/mL (suppressed) or ≥1000 copies/mL (not suppressed), please also see Appendix 1. Where the viral load data are missing at 12 months and the individual has died, the data will be left missing unless it is apparent from medical or death records that the person died due to high viral load or death was clearly AIDS related, in which case we will code them as not suppressed. The odds ratio at 12 months (and associated 95% CI) for <1000 copies/mL for TENDAI vs EUC will be estimated using a logistic regression model with the 12 month measure as the dependent variable, and trial arm as the independent variable, as well as the site stratification variable. We will fit two models, the one just described excluding baseline log viral load, and another including this as an independent variable, so will present odds ratio estimates both marginal and conditional with respect to baseline viral load. Moderation of treatment effects by sex will be assessed in these two final model backgrounds as outlined in Section 3.1.3.

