## 15. Recruitment Procedures.

Participants will be recruited by research assistants at the ART clinics at Marondera Hospital initially, and at Chitungwiza Central hospital. We will recruit from all patients identified as having a detectable viral load in the past 2 months, and from those at high risk of viral non-suppression (e.g. PLWH with missed appointments, those who have 'defaulted' medication, or those who self-report adherence problems). Potential participants will complete a brief study screener to assess for likely depression (see section 13, Participant Timeline). If they meet inclusion criteria, study recruiters will invite participants to complete the informed consent process and complete the baseline assessment. In those who screen positive for depression and are at high risk of viral non-suppression but have not had this confirmed by blood test in the last 2 months, baseline assessment will include a viral load test to ensure eligibility (see Baseline study visit). We will recruit from individuals initiated on ART for at least 6 months, which will allow for viral suppression to have been achieved if the person has been adherent to medication they are not resistant to, and to allow for the person to have gained some experience with the challenges of ART adherence.

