1.9 Sample size estimation

A sample size of 290 participants will provide 85% power to detect an absolute difference of 20% or more in achieving viral suppression (e.g. 45% in the EUC arm vs. 65% in the intervention arm) at 12-months follow-up. This is based on a two-sided Fisher's exact test with $\alpha = 0.05$ and allowing for 20% attrition. Pilot data showed a larger difference between arms (50% in the EUC arm vs. 75% in the intervention arm), suggesting this should be a conservative sample size estimate. For the secondary outcomes, this sample size will allow detection of an effect size of 0.37 or greater on the continuous depression scale (based on $\alpha = 0.05$, a two-sided test of difference between two independent means and the same level of attrition). The sample size will also provide 90% power to detect a 20% difference in the proportion with $\geq 90\%$ adherence as was seen in our pilot data (also Fisher's exact test, $\alpha=0.05$ and 20% attrition). This is based on our pilot data, national data (Dube et al) and other research (Ciesla et al, Safran et al).

2. Data analysis plan – Data description

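### The primary models for viral suppression omit ART line and baseline self-report adherence, both already collected; pre-specifying them is a low-cost gain in efficiency and robustness, not the repair of an error

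*SAP*

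**What the plan says.** SAP 3.1.1 fits two logistic models for suppression at 12 months. The first is specified "with the 12 month measure as the dependent variable, and trial arm as the independent variable, as well as the site stratification variable". The second adds baseline log viral load. Both odds ratios are presented, as marginal and conditional with respect to baseline viral load.

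The general rule in SAP 3.1 is: "Where the outcome variable is recorded at baseline it will generally be included in the analysis model as a covariate unless stated otherwise". For the binary primary outcome the baseline value is the same for everyone, because SAP 1.3.1 requires a viral load above 1000 copies/mL at entry. Baseline log viral load does vary, and the second model uses it.

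The baseline variables to be described in SAP 2.2 include "1st, 2nd or 3rd line ART prescribed". SAP 1.8.1 lists self-report and pharmacy refill adherence at baseline. None of these is in either primary model, and randomisation is stratified by site only.

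The protocol connects these variables with suppression. Section 6a names poor adherence, resistance and limited regimens as obstacles for people on ART. The conceptual model in section 8 routes the effect on suppression through adherence. Section 15 explains that the six-month entry rule allows time for suppression "if the person has been adherent to medication they are not resistant to".

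**The concern.** When an outcome's baseline value is constant, adjusting for it brings no precision, and any precision must come from other prognostic variables. Two plausible candidates are on file and unused. If they are prognostic, including them reduces the unexplained variation in the primary comparison and corrects for chance imbalance in them.

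There is also a missing-data aspect. SAP 3.1.4.5 lists baseline self-report adherence among the variables thought likely to predict missing 12-month viral load. Unless multiple imputation is triggered, the primary logistic model is a complete-case analysis without that variable.

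At stake are a few points of power at most, and some protection if dropout depends on adherence differently in the two arms.

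**Working it through.** **Inputs from the documents.** Two-sided 5% level (SAP 3.1). SAP 1.9: "A sample size of 290 participants will provide 85% power to detect an absolute difference of 20% or more in achieving viral suppression", with "45% in the EUC arm vs. 65% in the intervention arm" as the example, and 20% attrition. On the test: "This is based on a two-sided Fisher's exact test". Allocation is 1:1 (SAP 1.4).

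**Input not in the documents.** The prognostic strength of ART line and baseline adherence, and the share of participants on a later line. All gains below rest on assumed ranges.

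**1. The plan's own figure.** Evaluable: 290 × 0.8 = 232, or 116 per arm. Exact enumeration of Fisher's test at 0.45 v 0.65 gives 85.0%, so the stated 85% reproduces.

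The chi-squared approximation is closer to the planned logistic test:

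z = [0.20√116 − 1.96√(2 × 0.55 × 0.45)] / √(0.45 × 0.55 + 0.65 × 0.35) = (2.154 − 1.379) / 0.689 = 1.12, which is 87.0% power.

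Marginal odds ratio: (0.65 × 0.55) / (0.35 × 0.45) = 2.27.

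**2. Gain by formula.** If covariates explain a share R² of the within-arm outcome variance, the effective size per arm is 116 / (1 − R²).

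| Assumed R² | Total effective n | Power |
|---|---|---|
| 0% | 232 | 87.0% |
| 1% | 234 | 87.3% |
| 5% | 244 | 88.6% |
| 10% | 258 | 90.2% |
| 15% | 273 | 91.8% |

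**3. Gain by simulation.** 10,000 trials per row, n = 232, marginal rates held at 45% and 65%, Wald test of arm. The comparison is arm + site against arm + site + ART line + standardised adherence score. The share on a later line is 20% in the first three rows and 30% in the last two.

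| Later-line OR | Adherence OR per SD | R² | Arm + site | With both | Change (points) | Conditional OR |
|---|---|---|---|---|---|---|
| 1 | 1 | 0% | 87.2% | 86.8% | −0.4 | 2.27 |
| 0.67 | 1.2 | 1.4% | 87.1% | 87.2% | +0.2 | 2.30 |
| 0.5 | 1.5 | 5% | 86.3% | 87.6% | +1.4 | 2.38 |
| 0.5 | 2.0 | 11% | 87.4% | 90.4% | +2.9 | 2.52 |
| 0.33 | 2.0 | 14% | 86.9% | 90.8% | +3.9 | 2.59 |

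Changes are taken before rounding. The Monte Carlo standard error of each power figure is √(0.87 × 0.13 / 10,000) ≈ 0.3 points, so the first two rows show no clear change. The last column shows the conditional odds ratio moving away from 2.27 as covariates enter, which is why a standardised effect is needed.

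**4. Against the SAP's second model.** With baseline log viral load already in the comparator, and the standardised estimator as the test, the gain was about 0 (no prognostic value), 1 (weak), 2 (moderate, whichever direction adherence acts) and 4 points (strong). Type I error under the null was the same with and without the covariates. A separate null simulation, arm + site with and without them, gave 4.8% both ways.

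**5. Predictors of missingness, side by side.**
- Protocol 20c: baseline predictors of missing data go into the final models, with no exception for logistic ones.
- SAP 3.1 and 3.1.4.5: they go into the imputation model if multiple imputation is used; otherwise only into the PHQ-9, self-report adherence and log viral load models.

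An illustration under an assumed, fairly strong mechanism: no treatment effect, 290 randomised, about 20% missing, dropout depending on adherence in one arm only at a log-odds of 1.0 per SD, 4,000 runs. Type I error for arm + site was 6.1%, 7.4% and 7.6% in three scenarios of prognostic strength; with both covariates it was 5.3%, 5.7% and 5.1%. At a log-odds of 0.5 the inflation was negligible.

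**The case against.** The strongest case is that this is a preference. The plan meets its power target unadjusted. It gives a reason for the smaller model (a marginal odds ratio), and its second model carries the same covariates as the log viral load analysis in SAP 3.1.2. Even the direction of the adherence effect is uncertain: everyone enrolled is viraemic, so a participant reporting good adherence may be more likely to have resistance. Recruiting partly on self-reported adherence problems may also narrow the range of scores.

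Most of this stands, and it limits the claim. The uncertain direction does not remove the gain, because the model estimates the sign and the moderate gain was about the same either way. The wish for a marginal effect is met by standardisation.

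Three stronger readings might be inferred, and the documents support none of them:
- That power is wasted or the trial falls short. The 85% assumes an unadjusted test and reproduces; any forgone gain depends on strengths that nobody has stated and may be nil.
- That the SAP keeps covariates out of logistic models as a rule. SAP 3.1.4.5 excludes only predictors of missingness. The refill-adherence logistic model takes covariates similar to those of the PHQ-9 model, and the second primary model takes baseline log viral load.
- That chance imbalance makes the planned test invalid. Type I error is the same with and without adjustment when dropout is unrelated to the covariates.

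**Conclusion.** The omission is real and its consequence is modest. Pre-specifying ART line and baseline self-report adherence is worth about 0 to 4 points of power over a range from no to strong prognostic value. If the covariates are uninformative, the change is within simulation error. Those strengths, and the later-line share of 20% to 30%, are assumptions.

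The robustness benefit is separate and conditional: it matters if adherence predicts missing viral load, as the SAP anticipates, and most if it does so differently by arm. On that point the protocol and the SAP differ about the primary model and need to be reconciled. The planned analysis is valid and adequately powered on its own terms.

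**What to change.** In SAP 3.1.1:
- Specify one primary logistic model with arm, site, baseline log viral load, ART line (first v second or third) and baseline self-report adherence score, and state that it carries the primary test. The present text does not say which of its two models does.
- Report the effect by standardisation over the analysed sample (Stata margins after logit), so that it remains a population-level effect.
- Keep the arm-plus-site odds ratio as a supporting estimate.
- Align SAP 3.1 and 3.1.4.5 with Protocol 20c on whether baseline predictors of missingness enter the primary model.

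The cost is wording and one further Stata command, with no new data. Two consequences need attention. SAP 3.1.4.4 gives an imputation rule for baseline viral load, PHQ-9 and the two adherence measures but not for ART line, so a rule must be added. The analyses that reuse the primary model (moderation in 3.1.3, per-protocol in 3.1.4.7, sensitivity in 3.1.5) must be updated to match. Because SAP 3.1 has the trial statistician unblinded, the change should be fixed before outcomes are examined by arm.

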3.1.2 Analysis of secondary outcomes

The mean difference at 12 months (and associated 95% CI) in PHQ-9 between TENDAI and EUC, and a standardised effect size, will be estimated using a linear mixed effects model with the 4, 8 and 12 month measures as dependent variables; a random intercept at the participant level, with a random slope if warranted (assessed via likelihood ratio test); baseline PHQ-9, trial arm, time, and trial arm by time interaction terms as independent variables; as well as the site stratification variable. Note for this PHQ-9 outcome that while we will include all post-randomisation measures as dependent variables in the model in order to account for missing data, we will not present treatment difference estimates for 4 and 8 months (as per the trial objectives/outcomes).

Pharmacy refill data will be recoded into a binary variable: greater than or equal to 90% adherence in the past month or less than 90% adherence in the past month. Please refer to Appendix 1 – Scoring of outcome measures. The odds ratio at 4, 8 and 12 months (and associated 95% CI) for ≥90% pharmacy refill adherence between TENDAI and EUC will be estimated using a logistic mixed effects model with the 4, 8 and 12 month measures as dependent variables with a random intercept at the participant level, consideration of a random slope variable and similar independent variables as those described for PHQ-9. Please see the end of the section for some further details on the modelling of this binary variable.

Self-report adherence (Wilson et al) will be scored as described in the paper and modelled as described for PHQ-9.

The mean difference in log copies/mL of viral load at 12 months (and associated 95% CI) between TENDAI and EUC will be estimated using a linear regression model with the log viral load at 12 months as the dependent variable,

baseline log viral load and trial arm as independent variables, as well as the site stratification variable. Undetectable viral loads will be set to half the viral detection load limit of the Marondera Provincial Hospital lab machine, which is 15.

The logistic mixed effects models that will be used for the pharmacy refill adherence outcome are preferred on one hand because they have useful missing data properties. These will provide subject-specific effects. However, these subject specific conditional effects can be larger, sometimes appreciably larger, than either the crude odds ratio or the adjusted population-averaged marginal effects that would be obtained using Generalised Estimating Equation models (Hu et al). We will present both the conditional estimates from the mixed effects models, as well as the marginal estimates using GEE models with robust standard errors. We will focus on the conditional effects from the mixed models in the main paper, unless there is more than a two-fold difference, in which case we will focus on the GEE model results.

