### Secondary outcomes measures

1. Depression at 12 months post randomization measured as the total score on the Patient Health Questionnaire (PHQ-9).
2. Adherence to ART medication at 4, 8 and 12 months post randomization assessed as the proportion of the sample achieving at least 90% adherence in the past month assessed through pharmacy refill.
3. Self-reported adherence to ART medication at 4, 8, and 12-months post randomization assessed as the frequency of adherence in the past 30 days.
4. Viral load copies/mL at 12-months post-randomization follow-up measured as Mean log Viral Load.

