## 20a. Statistical methods

**Preliminary Analyses.** Variables will be summarized using appropriate summary statistics. In the preliminary analyses, we will also examine the equivalence of the random assignment of groups with regard to key baseline characteristics. This will involve non-statistical comparison of the treatment groups on sociodemographic characteristics, adherence-related variables, depression and biological markers (e.g., viral load).

**Primary and Secondary Outcome Analysis.** Effectiveness results will be reported following CONSORT guidelines (86) by intention to treat analysis and a-priori defined variables. These analyses will be conducted in Stata version 15 or IBM SPSS. For most analyses we will use generalized linear models (GLM) with properly-chosen (based on the distribution of dependent variable) link functions to analyze longitudinal data for each major study aim. The GLMs will be either be mixed effects models (e.g. for continuous PHQ-9 depression measure) or estimated using generalized estimating equations with robust standard error estimates (GEE e.g. for categorical viral load) to account for repeated measures of the outcomes. Time by treatment interaction effects will be included in models to allow the effects to differ at different time points. All tests will determine significance at  $\alpha = 0.05$ .

**Primary Aim.** It is hypothesized that the intervention will be associated with a significant increase in the proportion of those achieving viral suppression (primary outcome) compared to the EUC condition at 12 month follow up. Viral suppression is defined as viral load < 1000 copies/ml.

**Secondary Aims.** It is hypothesized that the intervention will be associated with significant reductions in depression (secondary outcome) and significant increases in the

proportion of the sample achieving 90% adherence compared to the EUC condition. For the depression outcome (assessed by independent assessor blind to randomization condition, using PHQ-9 continuous score), we will assess the difference in means between the stepped care-AD intervention and the EUC condition. For the adherence outcomes, we will compare the difference in proportion of those randomized to each condition meeting >90% adherence (assessed via pharmacy refill), and for self-reported adherence to ART medication at 4, 8, and 12-months post randomization (assessed as the frequency of adherence in the past 30 days).

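### The focus for pharmacy-refill adherence is chosen by an undefined two-fold rule between two different odds ratios, and neither is the difference in proportions that the protocol states

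*SAP*

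**What the plan says.** SAP 3.1.2 fits a logistic mixed model to refill adherence at 4, 8 and 12 months, "with a random intercept at the participant level, consideration of a random slope variable and similar independent variables" to those used for PHQ-9. An odds ratio is estimated at each of the three visits.

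The SAP prefers this model for its behaviour with missing data, and warns that "these subject specific conditional effects can be larger, sometimes appreciably larger, than either the crude odds ratio or the adjusted population-averaged marginal effects" from GEE. It then commits to reporting both: "We will present both the conditional estimates from the mixed effects models, as well as the marginal estimates using GEE models with robust standard errors". The choice of focus follows: "We will focus on the conditional effects from the mixed models in the main paper, unless there is more than a two-fold difference"; beyond that, the focus moves to the GEE estimate.

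The protocol words the outcome at population level. Section 12 has it "assessed as the proportion of the sample achieving at least 90% adherence in the past month assessed through pharmacy refill". Section 20a says of the adherence outcomes that "we will compare the difference in proportion of those randomized to each condition meeting" the threshold. The sample-size text (protocol 14, SAP 1.9) claims 90% power for a 20% difference in that proportion.

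**The concern.** Conditional and marginal odds ratios answer different questions, so the size of the gap between them gives no reason to prefer one. Under the rule, the observed gap decides which question the main paper answers.

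The rule also cannot be applied as written. It gives no scale and no visit, and the analyst who applies it is unblinded (SAP 3.1). Read visit by visit, it can put a conditional figure beside a marginal one in the same row of results.

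Protocol section 8 calls adherence a key secondary outcome, and section 6a says that effectiveness trials should inform policy-makers. For them the natural quantity is how many more people out of 100 reach 90% adherence. The SAP plans no between-arm estimate of that.

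**Working it through.** **The plan's own figures.** 290 randomised less 20% attrition leaves 232, or 116 per arm. The exact power of a two-sided Fisher test at 5% for 45% vs 65% is 85.0%, as stated. The 90% figure for adherence has no stated base rate. At 116 per arm, power is 89.8% for 60% vs 80% (or, by symmetry, 20% vs 40%) and 84.9% for 40% vs 60%. A 60% control rate is thus compatible with the stated power, but it is an assumption.

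**Size of the gap.** Assumptions: 60% control adherence, a normal random intercept with variance v, no covariates. The documents give neither the control rate nor v.

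1. The population proportion at linear predictor η is p(η) = ∫ expit(η + √v·z) φ(z) dz, computed by 101-point Gauss-Hermite quadrature.
2. Solve p(α) = 0.60, then set p1 = p(α + ln ORc), where ORc is the conditional odds ratio.
3. The marginal odds ratio is ORm = [p1/(1 − p1)] / (0.60/0.40).

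Example with ORc = 4 and v = 3.29 (latent ICC 0.50): α = 0.631 and p1 = 0.7898, so ORm = (0.7898/0.2102)/1.5 = 2.51. The ratio is 4/2.51 = 1.60 and the risk difference is 19.0 points.

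| ORc | v | ORm | ORc/ORm | Risk difference (points) |
|---|---|---|---|---|
| 2 | 1 | 1.79 | 1.12 | 12.8 |
| 2 | 2 | 1.67 | 1.20 | 11.5 |
| 2 | 3.29 | 1.57 | 1.27 | 10.2 |
| 2 | 5 | 1.49 | 1.34 | 9.1 |
| 4 | 1 | 3.25 | 1.23 | 23.0 |
| 4 | 2 | 2.83 | 1.41 | 20.9 |
| 4 | 3.29 | 2.51 | 1.60 | 19.0 |
| 4 | 5 | 2.24 | 1.78 | 17.1 |

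No row reaches two-fold, so the conditional odds ratio stays the focus throughout.

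**Scale.** The two readings of two-fold can disagree in either direction.

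- Proportions 45% vs 65% (ORm 2.27), random-intercept SD 2.5: ORc = 4.74. The odds ratio quotient is 2.09 (switch); the log odds ratio quotient is 1.90 (no switch).
- Proportions 50% vs 60% (ORm 1.50), SD 3: ORc = 2.41. The quotients are 1.61 (no switch) and 2.17 (switch).

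**Visit.** Take 60% control adherence and v = 5 throughout, with ORc falling from 6 at one visit to 4 at a later one. At the first visit p1 = 0.8116, so ORm = (0.8116/0.1884)/1.5 = 2.87 and 6/2.87 = 2.09. At the second, ORm = 2.24 and 4/2.24 = 1.78. Applied per visit on the odds ratio scale, the rule headlines 2.87 (marginal) and then 4.0 (conditional). The headline rises although both quantities fall. These are expected values for large effects (21 and 17 points), so they show what can happen, not how often.

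**Missing data.** The mixed model is valid under missing at random given its covariates. Ordinary GEE, without weighting or imputation, needs a stronger assumption. SAP 3.1 and 3.1.4.5 add baseline predictors of missingness only to the PHQ-9, self-report adherence and log viral load models, so the refill model does not gain them. Unless multiple imputation is used, moving the focus to GEE gives up the stated protection without replacing it, with 20% attrition planned for.

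**The case against.** A reader might infer that the rule hides a result, favours the intervention or invites false positives. The documents do not support that. Both estimates will be presented, the rule is written in advance, and the SAP itself explains that the two differ. A conditional odds ratio is generally further from 1, so a switch moves the focus to the smaller figure. With no treatment effect both odds ratios equal 1.

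A reader might also infer that the headline overstates the population effect nearly two-fold. A conditional odds ratio is not a biased estimate of anything; it misleads only if read as population-averaged. A gap close to two-fold needs both a large effect and strong heterogeneity. The pilot figures in protocol 6a (absolute increases of 25% and 14%) imply about 11 points, where the ratio is about 1.2 to 1.3 at variances 2 to 3.29. Baseline adjustment would tend to lower the residual variance further.

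The conflict with the protocol is limited too. Section 20a allows mixed or GEE models with a suitable link, so an odds ratio is not excluded, and SAP 2.7 promises descriptive proportions at each visit.

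All of this stands, and it reduces the point to emphasis and definition. It does not supply the missing scale or visit. Writing a result-dependent choice down in advance does not fix the estimand, and descriptive proportions are not a between-arm estimate with a confidence interval that allows for missing data.

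**Conclusion.** The point holds in limited form. The focus for one secondary outcome depends on an observed gap between two different estimands, through a trigger with no stated scale or visit. The contrast named in protocol 20a and used for power is not among the planned between-arm estimates.

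At 60% control adherence and variances of 1 to 5, the conditional odds ratio exceeds the marginal one by a factor of 1.12 to 1.34 when it equals 2, and 1.23 to 1.78 when it equals 4. These figures rest on an assumed control rate, an assumed variance and a normal random intercept without covariates. The trigger's lack of definition does not depend on them. The primary outcome is unaffected.

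**What to change.** Delete the two-fold rule from SAP 3.1.2. Name one headline estimand for 4, 8 and 12 months: the between-arm difference in the proportion with at least 90% refill adherence, with 95% CI. Obtain it from the planned mixed logistic model by predicting for every participant under each arm, integrating over the random effects rather than setting them to zero, averaging over the covariates, and using a delta-method or bootstrap interval. This gives the protocol's contrast and keeps the likelihood-based handling of missing visits. Report the conditional and GEE odds ratios, both already planned, as supporting results at every visit.

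If the team prefers an odds ratio as headline, naming one type in advance for all visits would also remove the data-driven choice, but would not supply the protocol's contrast.

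The cost is a change of SAP wording and one post-estimation step in Stata, with no new data. The headline may look less large than the conditional odds ratio.
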